1. INTRODUCTION

This statistical analysis plan provides guidelines for the final analysis and presentation of results for the DOMINO-HD study. This plan, along with all other documents relating to the analysis of this study, will be stored in the Statistical Analysis Master File electronically. Location:

S:/Centre for Trials Research/Research/Mixed Studies/DOMINO/eTMF/8.0 Data Management & Statistics/8.5 Statistics/8.5.1 Statistical Analysis Plan

2. BACKGROUND

2.1 RATIONALE AND RESEARCH QUESTION

There are not many studies assessing the combined impact of lifestyle factors such as diet alongside direct longitudinal measures of physical activity and sleep on the progression and severity of HD, and none which have attempted to combine detailed genetic information with these modifiable factors.

DOMINO-HD is a 12-month observational study which aims to recruit participants from five clinical sites across Europe, with a combined target of 300-450 participants (at least 60, but no more than 90, participants per site). It utilises a digital platform developed during phase 1 of the study and a range of self-reported lifestyle questionnaires and wearable activity trackers (see the study protocol for more details) to gather phenotypical lifestyle data. As all participants are recruited from Enroll-HD (a global research platform), we will establish the feasibility of linking the DOMINO-HD lifestyle dataset to Enroll-HD clinical outcomes and where possible genome-wide association study (GWAS) data to explore their interplay with HD symptom severity. Ultimately, we aim to use these data to inform predictive outcome modeling and development of interventions aiming to slow the progression of HD or at the very least minimise functional impact of the disease.

TPL/008/2(v1.0)

2.1.1 Enroll-HD

Enroll-HD is a worldwide research platform which serves as the basis of a longitudinal observational study of HD families and provides an infrastructure to support clinical trials. Enroll-HD data are available to every researcher working with HD on reasonable request. All DOMINO-HD participants are also required to have consented to participation in Enroll-HD. Data from the annual Enroll-HD observational assessments will be merged with data obtained from the DOMINO-HD lifestyle assessments, including specific dietary questionaries and wearable activity tracker data to form a comprehensive lifestyle and clinical dataset in this population.

2.2 OBJECTIVES

The primary objective (and the focus of this statistical analysis plan) is to establish the feasibility of linking lifestyle factors and genetic risk factors to explore their interplay with HD symptom progression and severity.

3. STUDY MATERIALS

3.1 STUDY DESIGN

A consortium-led observational, prospective cohort study examining the effect of long-term (12 months) lifestyle factors (diet, sleep, physical activity), combined with genomic data, on the progression of HD symptoms. Participants will be recruited from Enroll-HD.

3.2 RANDOMISATION

Not applicable as DOMINO-HD is an observational study.

3.3 SAMPLE SIZE

Based on previous clinical trials with similar assessments and participant burden (see the protocol for more details), it is estimated that a minimum of 60 participants (and up to 90) per site will be required. This will result in a total of 300-450 participants across the five clinical sites. With a sample size of 300, conservative assumptions about the impact of the propensity score weighting, and a type I error rate of 0.05, we will have 80% power to detect effect sizes that are at least as large as 0.23 for each environmental measure when they are modelled as continuous predictors. This represents the minimum change in the HD composite outcome that would be detected as statistically significant with 80% power for a 1-unit change in the

TPL/008/2(v1.0)

DOMINO-HD: STATISTICAL ANALYSIS PLAN

environmental measure, suggesting the study has reasonable power for small to moderate effects.

3.4 FRAMEWORK

In people with HD, we will assess how lifestyle factors are related to the progression and severity of the disease.

3.5 INTERIM ANALYSES There are no interim analyses planned.

3.5.1 PLANNED SAMPLE SIZE ADJUSTMENT Not applicable.

3.5.2 STOPPING RULES Not applicable.

3.6 TIMING OF FINAL ANALYSIS Outcomes will be analysed once the final dataset becomes available.

3.7 TIMING OF OUTCOME ASSESSMENT

Outcome measures will be assessed at their corresponding time point (i.e., baseline at the time of recruitment, follow-up at the end of the 12-month period).

4. STATISTICAL PRINCIPLES

4.1 LEVELS OF CONFIDENCE AND P-VALUES

95% confidence intervals will be reported. All p-values will be compared to 5% level of significance.

4.1.1 ADJUSTMENT FOR MULTIPLICITY

None due to the exploratory nature of the study.

4.2 PROTOCOL DEVIATIONS

4.2.1 DEFINITION OF PROTOCOL DEVIATION

See protocol for full details. Examples of deviations include errors in applying inclusion/exclusion criteria and missed follow-up assessments due to error. TPL/008/2(v1.0) CONFIDENTIAL Page 7 of 41

4.2.2 PRESENTATION OF PROTOCOL DEVIATIONS These will be tabulated, with reasons (if given).

4.3 ANALYSIS POPULATION

All participants with available outcome data will be included in the primary analysis. As part of sensitivity analyses, a complete-case analysis (excluding participants with incomplete data) will be performed.

5. STUDY POPULATION

5.1 SCREENING DATA

Eligibility data: potential participants will be identified from registered Enroll-HD participants. If an individual is considered suitable for DOMINO-HD, but is not registered in Enroll-HD, it is acceptable to be recruited to both at the same time.

Informed consent: those meeting eligibility criteria and providing informed consent will be registered as study participants and assigned a unique study identification number prior to baseline data collection.

Safety data: the study is an observational study where no participant will receive any kind of intervention. We do not expect adverse events and there is no need for the participants to undergo any safety assessments.

5.2 ELIGIBILITY

Numbers eligible (as a proportion of those screened), consented (as a proportion of those eligible), and followed up (as a proportion of those consented) will be reported descriptively for the entire study and by site.

5.3 RECRUITMENT

Participants will be recruited from five current Enroll-HD sites across Europe. Up to 90 participants will be recruited from each site (minimum of 60).

5.4 WITHDRAWAL/FOLLOW UP

5.4.1 LEVEL OF WITHDRAWAL

Participants have the right to withdraw consent for participation in any aspect of the study at any time. If a participant initially consents but subsequently withdraws from the study, clear distinction must be made as to what aspect of the study the participant is withdrawing from.

TPL/008/2(v1.0)

DOMINO-HD: STATISTICAL ANALYSIS PLAN

Data collected prior to participant withdrawal will be used, unless the participant specifically asks that they are not.

These aspects could be:

- 1. Partial withdrawal from further data collection (e.g., some of sample collection, questionnaires, clinical assessments)
- 2. Complete withdrawal from further data collection
- 3. Withdrawal of permission to use data already collected

A participant will be deemed lost to follow-up if they do not attend the 12-month assessment, within a period of 8 weeks of the scheduled assessment (adhering to the Enroll-HD protocol). As all participants will be participants of Enroll-HD, we expect to obtain a proportion of 12-month assessment data for all participants unless they are lost to follow-up in the Enroll-HD study.

5.4.2 TIMING OF WITHDRAWAL

The timing and level of any withdrawals will be tabulated.

5.4.3 REASONS FOR WITHDRAWAL

Due to the participants' involvement in Enroll-HD, we do not anticipate a high rate of loss of follow-up from the study. Potential reasons for withdrawal include withdrawal of consent by the participant, or loss to follow-up as defined above. Reasons for withdrawal, if known, will be collected and tabulated.

5.4.4 PRESENTATION OF WITHDRAWAL/LOSS TO FOLLOW-UP

Numbers and percentages of withdrawal/loss to follow-up will be reported and tabulated for the entire study and by site.

5.5 BASELINE PARTICIPANT CHARACTERISTICS

5.5.1 LIST OF BASELINE DATA

The full list of variables in database can be found in the data dictionaries (S:\Centre for Trials Research\Research\Mixed Studies\DOMINO\eTMF\8.0 Data Management & Statistics\8.1 Data Management\8.1.3 Metadata\Data Dictionaries)

Physical activity data: Data from the Fitbit Charge 4 activity tracker will be collated for all participants across all clinical sites to provide a summary overview of physical activity across the cohort. Step counts from FitBit and Metabolic Equivalent of Task (MET)-minutes from the International Physical Activity Questionnaire (IPAQ) will be used as continuous variables, when controlling for bias, and will be dichotomised, when assessing their effect on the TPL/008/2(v1.0) CONFIDENTIAL Page 9 of 41

DOMINO-HD: STATISTICAL ANALYSIS PLAN

progression of the disease. Scores from the Brunel Physical Activity Questionnaire and Lifetime Total Physical Activity Questionnaire (LTPAQ) will be used to report summary statistics based on these scores and be compared (e.g. with scatter plots and correlation coefficients) to FitBit step counts, and whether it is feasible to use these scores interchangeably. Percentage of missing values will be reported. The LTPAQ is an optional questionnaire, so reports of missing values should include which have missing components, and which are entirely missing (e.g. due to optional non-completion from the participant), if that information is available.

Diet data: Information from a modified Food Frequency Questionnaire (FFQ) will be collated to produce a summary overview of nutrition. Descriptive summary statistics from Malnutrition Universal Screening Tool (MUST) data will be reported, to understand the percentage of people who are malnourished at baseline. Additionally, summary descriptive statistics will be reported for data from a Swallowing Screening Tool (EAT10) about the number of people who have swallowing difficulties at baseline. Finally, summary statistics for BMI, calf and waist circumference will be reported at baseline. Percentage of missing values will be reported.

Sleep data: Sleep data obtained from activity trackers worn will be collated to generate a summary overview. These variables will be used as continuous covariates when controlling for bias, and will be dichotomised when assessing their effect on the progression of the disease. Data from the HD Sleep Questionnaire will be summarised and reported. These will be compared to data from activity trackers (e.g. using Pearson correlation or scatter plots, or other methods if appropriate), to assess consistency between self-reported and tracker data. Percentage of missing values will be reported. Linked Enroll-HD data from all sites will be summarised (e.g., demographic data, listed in Table 1). Percentage of missing values will be reported. Data from HD-ProTriad (severity of the disease) will be summarised and descriptive statistics will be reported. Percentage of missing values will be reported.

Scoring methods for the questionnaires mentioned above are presented in Appendix D.

Variable Name	Description
Age	Age at baseline (at the first visit)
HD-Stage	- Late pre-manifest (LPM): No motor onset, age \geq 18yrs, CAG \geq 36, CAP > 80

Canolfan Ymchwil Treialon

DOMINO-HD: STATISTICAL ANALYSIS PLAN

	- Stage 1: $10 < \text{TFC} \le 13$
	- Stage 2: $6 < \text{TFC} \le 10$
	- Stage 3: TFC ≤ 6
Sex	Sex assigned at birth (male/female)
CAG	CAG repeat length
САР	CAG-age product, defined as Age*(CAG-30)/6.49
race	Ethnicity
hddiagn	Age at clinical HD diagnosis
sxraterm	Rater's judgement of initial major symptom
ccdep	Has depression (includes treatment with antidepressants with or without a formal diagnosis of depression) ever been a part of the participant's medical history?
hdcat_I	Participant category (latest)
cmtrt_atc	Pharmacotherapy — ATC code
cmdostot	Pharmacotherapy – Total daily dose
cmenrf	Pharmacotherapy – Ongoing
cmtrt	Non-Pharmacologic Therapies – Therapy
cmfrq	Non-Pharmacologic Therapies – Number of times
cmdosfrq	Non-Pharmacologic Therapies – Frequency
cmenrf	Non-Pharmacologic Therapies – Ongoing
cmcar	Nutritional Supplements – Type
cmtrtatc	Nutritional Supplements – ATC code(s)
cmenrf	Nutritional Supplements – Ongoing
mhbodysy	Comorbid Conditions – Body system code

TPL/008/2(v1.0)

Canolfan Ymchwil Treialon

DOMINO-HD: STATISTICAL ANALYSIS PLAN

mhterm_modify	Comorbid Conditions – Modified term (coded with ICD10)
mhenrf	Comorbid Conditions – Ongoing
height	Height (cm)
weight	Weight (kg)
bmi	BMI
alcab	Does the participant currently drink alcohol?
alcunits	Units of alcohol per week
tobab	Does the participant currently smoke?
packy	Pack-years
cafab	Current caffeine use?
cafpd	Do you drink more than 3 cups of coffee, tea and cola drinks combined per day?
mar	Drug use for non-medical reasons? – Abuse
marfrq	Drug use for non-medical reasons? – Frequency
isced	ISCED education level
jobclas	Employment (status)
motscore	Motor Score (TMS)
ocularh	Ocular pursuit – Horizontal
ocularv	Ocular pursuit – Vertical
sacinith	Saccade initiation – Horizontal
sacinity	Saccade initiation – Vertical
sacvelh	Saccade velocity – Horizontal
sacvelv	Saccade velocity – Vertical
dysarth	Saccade velocity – Dysarthria

TPL/008/2(v1.0)

Canolfan Ymchwil Treialon

DOMINO-HD: STATISTICAL ANALYSIS PLAN

tongue	Saccade velocity – Tongue protrusion
fingtapr	Finger taps – Right
fingtapl	Finger taps – Left
prosupr	Pronate supinate (hands) – Right
prosupl	Pronate supinate (hands) – Left
luria	Pronate supinate (hands) – Luria
rigarmr	Rigidity (arms) – Right
rigarml	Rigidity (arms) – Left
brady	Rigidity (arms) – Bradykinesia body
dysttrnk	Maximal dystonia – Trunk
dystrue	Maximal dystonia – RUE (right upper extremity)
dystlue	Maximal dystonia – LUE (left upper extremity)
dystrle	Maximal dystonia – RLE (right lower extremity)
dystlle	Maximal dystonia – LLE (left lower extremity)
chorface	Maximal chorea – Face
chorbol	Maximal chorea – BOL (bucco-oral-lingual)
chortrnk	Maximal chorea – Trunk
chorrue	Maximal chorea – RUE (right upper extremity)
chorlue	Maximal chorea – LUE (left upper extremity)
chorrle	Maximal chorea – RLE (right lower extremity)
chorlle	Maximal chorea – LLE (left lower extremity)
gait	Gait
tandem	Tandem walking

TPL/008/2(v1.0)

Canolfan Ymchwil Treialon

DOMINO-HD: STATISTICAL ANALYSIS PLAN

retropls	Retropulsion pull test
diagconf	Diagnostic confidence level (DCL)
tfcscore	UHDRS TFC – Functional score
fascore	UHDRS function – functional assessment score
sdmt1	Core Cognitive Assessment – Total correct
swrt1	Core Cognitive Assessment – Total correct
anxscore	HADS-SIS – Anxiety subscore
hads_depscore	HADS-SIS – Depression subscore
irrscore	HADS-SIS – Irritability subscore
outscore	HADS-SIS – Outward irritability subscore
inwscore	HADS-SIS – Inward irritability subscore
tug	Physiotherapy – Timed "up and go" performed
tugl	Physiotherapy – Total time
scst	Physiotherapy – 30 sec chair stand test performed
scst1	Physiotherapy – Number of times the participant stands in 30 seconds
depscore	PBAs – Depression
irascore	PBAs – Irritability and aggression
psyscore	PBAs – Psychosis
aptscore	PBAs – Apathy
exfscore	PBAs – Executive function
pcs	SF-12 – Physical Component (PCS)
mcs	SF-12 – Mental Component (MCS)

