6. ANALYSIS

6.1 OUTCOME DEFINITIONS

6.1.1 PRIMARY OUTCOME(S)

The primary objective of this study is to establish the feasibility of linking lifestyle, clinical and genetic data and to explore their interplay with HD symptoms and severity.

We will explore the proportions of recruited participants with linked DOMINO-HD and Enroll-HD clinical data as well as linked GWAS data. We will also explore follow-up rates and lifestyle and wearable activity tracker data completeness and balance statistics in important variables. Our data will be used to provide progression criteria recommendations for future studies in this field.

Aspects of feasibility which will be assessed are:

- Completeness of key lifestyle questionnaires (at baseline: HD Pro-Triad, FFQ, LTPA, Sleep, IPAQ, Relationship) data [>80% returned with >80% completeness = feasible, >60% returned with >60% completeness = changes required, <60% returned or <60% completeness = not feasible]
- Completeness of activity tracker data [>70% feasible, 50-70% changes required, <50% not feasible]
- % participants linked with Enroll-HD clinical data [>80% feasible, 60-80% changes required, <60% not feasible]
- % participants linked with GWAS data [>60% feasible, 40-60% changes required, <40% not feasible]
- % participants with follow-up at 12m [>70% feasible, 50-70% changes required, <50% not feasible]
- Feasibility of balancing important covariates. Adequate balance of baseline covariates is achieved when the maximum Kolmogorov-Smirnov (KS) value is equal to or below 0.1. However, as the recommendation is for 60-80 observations per covariate per treatment

TPL/008/2(v1.0)

Centre for Trials Research Canolfan

Ymchwil Treialon

DOMINO-HD: STATISTICAL ANALYSIS PLAN

group (Markoulidakis, Holmans, et al., 2021), the feasibility of achieving balance should be determined alongside the available sample size.

• Agreement between questionnaire and activity tracker data

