6.2 ANALYSIS METHODS

The main modifiable lifestyle factors we are interested in, in terms of their impact on cUHDRS progression, are sleep, diet, and physical activity.

1. Sleep:

Total minutes of sleep are available per participant through the extracts from activity trackers. As there is no evidence in the literature about the minimal time of sleep required for individuals with HD, we will utilise the first tertile to dichotomise the participants into two categories (those with more sleep than two thirds of the sample vs. the rest). Dichotomisation based on the first quartile and the median, respectively, will be used as an alternative, to assess the sensitivity of our findings. Sleep efficiency – defined as the ratio of sleep duration (average total sleep time, TST) to duration in bed (average total time in bed, TBT) – will also be considered. TBT and TST will be extracted from FitBit. Alternatively, propensity score (PS) weighting for continuous treatment variables, as described in section 6.2.2, could be explored. The first tertile will be used as a cut-off point for the primary analysis, dichotomisation on the first quartile and the median, respectively, will also be explored, to understand the sensitivity of our findings.

The HD sleep questionnaire contains 45 questions that focus on different sleep-related issues such as duration, quality of sleep, abnormal nocturnal behaviour and quality of life. Variables emerging from the HD sleep questionnaire will be reported descriptively. A sleep disturbance score will be derived from a sub-set of the questions, namely 4-11, 14, 15, 18, 19, 14, 27, 28, 34 (Goodman et al., 2010).

Self-reported total sleep time (calculated from questions 1 and 2 of the HD sleep questionnaire) will be compared with average total sleep time from activity trackers. The values for sleep efficiency from activity trackers and sleep questionnaires (sleep disturbance) will also be assessed for correlation (association of high sleep disturbance with low sleep efficiency) and reported.

2. *Diet*:

TPL/008/2(v1.0)

DOMINO-HD:	STATISTICAL ANALYSIS PLAN
------------	---------------------------

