Appendix D: Scoring of questionnaires

Questionnaire	Scope	Scoring
IPAQ	Assessing the types of intensity of physical activity and sitting time that people do as part of their daily lives, and using this time to estimate total physical activity in MET-minutes/week and time spent sitting.	To compute the MET-minutes using IPAQ the following formula is used: $8 \times (minutes \ of \ vigorous \ activity \ per \ day) \times (\# \ of \ days)$ + $4 \times (minutes \ of \ moderate \ activity \ per \ day) \times (\# \ of \ days)$
Brunel	The Brunel lifestyle physical activity questionnaire consists of 9 questions regarding the duration and severity of planned (6) and unplanned (3) physical activity.	 + 3.3 × (minutes of more than 1' walking per day) × (# of days) Each question receives 1-5 points, depending on the frequency of the activity in question (e.g. 1 = Not at all, 5 = Highly). Planned physical activity is defined as, " any activity that is scheduled into a daily routine, which may enhance your health, fitness, or well-being" (e.g. brisk walking,

TPL/008/2(v1.0)

CONFIDENTIAL

Page 34 of 41

Canolfan Ymchwil Treialon

DOMINO-HD: STATISTICAL ANALYSIS PLAN

		cycling). Unplanned physical activity is defined as any form of physical activity "excluding pre-planned physical activity" (e.g. heavy housework, playing with children).
		Factor scores for planned and unplanned dimensions of physical activity are calculated by adding scores from items 1–6 (planned) and 7–9 (unplanned), then dividing them by six and three, respectively. Factor scores range from 1 to 5, with higher scores indicating higher engagement in physical activity.
LTPAQ	Estimating the average physical activity of the participant during their lifetime.	Categories of intensity Category 1: Requires only sitting with minimal walking. Category 2: Requires a minimal amount of physical effort such as standing and slow walking. There is no increase in heart rate and there is no perspiration.

TPL/008/2(v1.0)

Canolfan Ymchwil Treialon

DOMINO-HD: STATISTICAL ANALYSIS PLAN

FPL/008/2(v1.0)	CONFIDENTIAL	Page 36 of 41
Modified FFQ	The FFQ requires respondents to report frequency of consumption of a predefined lis	1 1 1
		in the LTPQA Comprehensive Users' Guide.
		hours/week. The MET corresponding to each activity are listed
		that activity. The resulting data would be denoted as MET-
		multiplying the hours spent by the estimated metabolic cost of

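### Questionnaire–tracker agreement is a primary feasibility aspect, but the only methods the SAP names for it, scatter plots and correlation, measure association rather than agreement

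*SAP*

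**What the plan says.** Section 6.1.1 gives as one primary feasibility aspect "Agreement between questionnaire and activity tracker data". No statistic or threshold follows. Neighbouring items have cut-offs, for example "Completeness of activity tracker data [>70% feasible, 50-70% changes required, <50% not feasible", and covariate balance is tied to a maximum KS of 0.1.

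The methods are scattered over other sections:

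- **Brunel and LTPAQ against steps** (5.5.1, physical activity): the scores will be "compared (e.g. with scatter plots and correlation coefficients) to FitBit step counts, and whether it is feasible to use these scores interchangeably".
- **Sleep questionnaire against tracker** (5.5.1, sleep): "e.g. using Pearson correlation or scatter plots, or other methods if appropriate), to assess consistency between self-reported and tracker data".
- **Total sleep time** (6.2, Sleep): "Self-reported total sleep time (calculated from questions 1 and 2 of the HD sleep questionnaire) will be compared with average total sleep time from activity" (that is, the FitBit). No method is named.
- **Sleep efficiency against sleep disturbance** (6.2, Sleep): these "will also be assessed for correlation (association of high sleep disturbance with low sleep efficiency) and reported".

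Appendix D sets the Brunel scale: "Factor scores range from 1 to 5, with higher scores indicating higher engagement in physical activity". It describes LTPAQ as an estimate of average activity over the participant's lifetime, in hours per week or MET-hours per week. Table 5 gives step count as a daily number at baseline.

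The SAP names no mean difference with limits of agreement, ICC, concordance coefficient or kappa for any of these comparisons.

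**The concern.** Agreement asks whether two measures give the same value, or put a person in the same group. Interchangeability asks whether one can stand in for the other. Correlation asks only whether they rise and fall together. The SAP poses the first two questions and names a tool for the third.

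The gap takes two forms:

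- **Different units.** Brunel and LTPAQ share neither a unit nor, for LTPAQ, a time frame with daily steps. Even a high correlation would not show that either could replace step count.
- **Same unit.** Self-reported and tracker sleep time are both in minutes, so systematic over- or under-reporting is well defined and matters. Pearson's r cannot detect it.

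Section 6.1.1 says the data will feed progression criteria recommended for later studies. A statement on agreement that rests on correlation would be carried into them.

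**Working it through.** The SAP gives no figure for agreement, so there is none to reproduce. The check compares what r registers with what agreement measures register.

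**Assumed inputs (none is in the SAP):** tracker and self-reported sleep time jointly normal, SD s = 60 min for both; r = 0.70 or 0.80; constant over-report b from 0 to 60 min. From the SAP: sleep is dichotomised at a sample tertile (6.2), taken here as the lowest third.

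**Step 1. Does r respond to bias?** In a simulated sample of 300 pairs r was 0.807. It was still 0.807 after adding 60 min to every self-report, and after multiplying every self-report by 1.5.

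**Step 2. Do agreement measures respond?**

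- Limits of agreement = b ± 1.96 × s√(2(1 − r)). At r = 0.70 the SD of differences is 60 × √0.6 = 46.5, so b ± 91. At r = 0.80 it is 60 × √0.4 = 37.9, so b ± 74.
- Concordance = 2rs² / (2s² + b²). At r = 0.70, b = 45: 5040 / (7200 + 2025) = 0.55. At r = 0.80, b = 60: 5760 / (7200 + 3600) = 0.53.

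**Step 3. Classification if the tracker's lower-tertile cut is applied to self-report.** The cut is z = −0.431 for the tracker and −0.431 − b/60 for self-report. For r = 0.70, b = 45:

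- P(self-report below cut) = Φ(−1.181) = 0.119
- P(both below) = 0.099
- Discordant = 0.333 + 0.119 − 2 × 0.099 = 0.255
- Chance agreement = 0.333 × 0.119 + 0.667 × 0.881 = 0.627
- Kappa = (0.745 − 0.627) / (1 − 0.627) = 0.32
- Share of tracker-defined short sleepers found = 0.099 / 0.333 = 30%

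| r | Bias (min) | Limits (min) | Concordance | Discordant | Kappa | Short sleepers found |
|---|---|---|---|---|---|---|
| 0.70 | 0 | −91 to +91 | 0.70 | 23% | 0.48 | 66% |
| 0.70 | 30 | −61 to +121 | 0.62 | 24% | 0.40 | 41% |
| 0.70 | 45 | −46 to +136 | 0.55 | 25% | 0.32 | 30% |
| 0.80 | 0 | −74 to +74 | 0.80 | 19% | 0.58 | 72% |
| 0.80 | 60 | −14 to +134 | 0.53 | 27% | 0.26 | 22% |

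**Step 4. Classification if each measure is cut at its own lowest tertile.** A constant shift or positive rescaling then moves nobody, and the result depends on r alone. This is also the calculation that applies to measures in different units.

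| r | Discordant | Kappa |
|---|---|---|
| 0.5 | 30% | 0.32 |
| 0.7 | 23% | 0.48 |
| 0.8 | 19% | 0.58 |
| 0.9 | 13% | 0.71 |

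**The case against.** **The SAP does not prescribe correlation.** The activity list is introduced by 'e.g.', the sleep list leaves room for "using Pearson correlation or scatter plots, or other methods if appropriate", and total sleep time is simply to be compared. A scatter plot of two measures in minutes can show a constant shift by eye. This stands: the SAP fails to fix an agreement method and exemplifies an unsuitable one, but forbids nothing better.

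**Correlation is right for one comparison.** For sleep efficiency against sleep disturbance the stated aim is association. That item needs no change.

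**Reporting bias does not explain the Brunel and LTPAQ problem.** Over-reporting is undefined between a 1–5 score and a step count. This also stands: the bias argument belongs to same-unit pairs, and for Brunel and LTPAQ the defect is that the measures are not commensurable.

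**A reader might infer that bias would put most participants in the wrong exposure group.** The documents do not support that. The SAP cuts sleep and MET-minutes at sample quantiles, and nowhere proposes applying the tracker's cut to self-report. Under own-sample cuts a constant bias has no effect. Even with the tracker's cut imposed, about 25–27% of all participants are discordant in the two most biased scenarios; what falls to 22–30% is the share of short sleepers detected.

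**A reader might also infer that a criterion could be passed wrongly.** The agreement item has no threshold, so there is no pass to be obtained.

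**The use is descriptive and the study exploratory.** The sleep exposure comes from the tracker, and replacing a covariate with much missing data (6.3) is only a possibility. This limits the stakes, but agreement is still listed under the primary outcome.

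**Conclusion.** The concern holds as a mismatch between the question asked and the methods named. Scatter plots and correlation are the only tools mentioned, as open-ended examples, and correlation cannot establish agreement or interchangeability. For Brunel and LTPAQ against steps this follows from the units alone and needs no assumption.

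For total sleep time, the insensitivity of r to constant or proportional bias is a mathematical fact. Its size in this cohort is unknown. On the assumed SD of 60 min and r = 0.80, a 60-minute bias lowers concordance from 0.80 to 0.53 with r unchanged. The kappas of 0.32 and 0.26 for the biased cases hold only if the tracker's cut-point is applied to self-report. With own-sample tertiles, kappa is 0.48 at r = 0.70 and 0.58 at r = 0.80 whatever the constant bias.

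The lifestyle effect estimates are not directly affected. What is affected is the conclusion on one primary feasibility aspect and any recommendation built on it.

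**What to change.** 1. For self-reported against tracker total sleep time, and for IPAQ against FitBit MET-minutes if that comparison is made, report the mean difference with 95% limits of agreement and an ICC or concordance coefficient with 95% CI. Put IPAQ and FitBit MET-minutes on the same time base first.
2. For activity measures in different units (Brunel and LTPAQ against steps), report cross-classification and kappa on the groups used in the analysis, stating beforehand how each questionnaire score is cut. Remove 'interchangeably' from 5.5.1.
3. In 6.1.1, state that the agreement item is judged on these statistics. If it is to be graded like the items beside it, give the limits there.
4. Keep correlations and scatter plots as description, including the efficiency–disturbance comparison as planned.

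The cost is revised SAP wording and a few extra lines of analysis. No new data are needed.
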